2.1 Primary Objective

The primary objective of this investigation is to evaluate improvement of benign prostatic hyperplasia (BPH) symptoms as assessed by the International Prostate Symptom Score (IPSS) after prostate artery embolization (PAE) with Embosphere® Microspheres in 20 patients with 24 months follow-up.

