3.2 Exclusion Criteria

Patients that meet any of the following exclusion criteria will not be eligible for this study.

1. History of prostate, bladder or rectal malignancy. Biopsy proven urethral cancer.
2. History of rectal disease
3. Neurogenic bladder disorder due to multiple sclerosis, Parkinson's disease, spinal cord injury, diabetes, etc., as demonstrated on urodynamic testing.
4. Detrusor muscle failure, urethral stenosis, or urinary obstruction due to causes other than BPH, as demonstrated on urodynamic testing
5. Bladder diverticula greater than 5 cm or bladder stones greater than 2 cm
6. Cystolithiasis within the past three months
7. Baseline serum creatinine greater than 1.8
8. Evidence of tortuous or atherosclerotic blood vessels
9. Presence of collateral vessel pathways potentially endangering normal territories during embolization that cannot be bypassed with the microcatheter
10. Active urinary tract infection, interstitial cystitis, or prostatitis within the last 5 years
11. Coagulation disturbances not normalized by medical treatment
12. Allergy to iodinated contrast agents not responsive to steroid premedication regimen
13. Previous radical pelvic or rectal surgery, or pelvic irradiation
14. Prior surgical prostate intervention
15. Treatment with beta-blocker, antihistamine, anticonvulsant, or antispasmodic medication within 1 week of treatment UNLESS there has been a stable voiding pattern while medicated with the drug(s) for 6 months
16. Use of prostate active medications, including alpha blockers, anti-cholinergics, androgens, anti-androgens, gonadotropins-releasing hormonal analogs, PDE5-inhibitors, 5-alpha reductase inhibitors within 2 months of intervention, unless the medication is necessary to avoid symptom exacerbation and disability, in this case medication should not be initiated or dose adjusted within 1 month of study enrollment and dose should not be adjusted during the study period
17. Interest in future fertility
18. Mental condition or disorder that interferes with participants' ability to provide written informed consent

19. Current severe or uncontrolled disease (metabolic, hematologic, renal, hepatic, pulmonary, neurologic, cardiac, infectious or gastrointestinal) that in the Investigator's judgment makes the patient unsuitable for trial inclusion due to increased risk of complications
20. Known immunosuppression
21. Life expectancy less than 6 months

4. Study Design

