This is a phase I/II, single center, prospective, single arm, investigational study to evaluate the safety and efficacy of prostate artery embolization (PAE) for treatment of severe lower urinary tract symptoms (LUTS) related to benign prostatic hyperplasia (BPH) in patients with prostate size between 40 and 300 cm³ that have either failed or are intolerant to medical management. Patients will be considered enrolled in the study once they have provided informed consent. A total of 20 patients will be enrolled in the single treatment arm of the study. Treated participants will be followed for no less than 24 months.

The study will involve a screening period in which patient eligibility is determined. Once eligibility is confirmed, patients will undergo PAE with Embosphere Microspheres within 4 weeks of baseline prostate ultrasound. Following treatment, patients will return for follow-up visits at 1, 6, 12, and 24 months post PAE. At each of these visits, patients will complete the International Prostate Symptom Score (IPSS) and International Index of Erectile Function (IIEF) questionnaires, undergo a physical exam, transrectal prostate ultrasound, transabdominal prostate ultrasound, uroflowmetry and laboratory evaluations, and medication and adverse event reviews.

The primary objective of the study will be improvement of BPH symptoms as assessed by the IPSS questionnaire. Patients will continue to be followed according to the institutional standard of care follow-up schedule after they complete the study.

Safety will be evaluated throughout the study by assessing adverse events and findings on physical examination. Concomitant medication usage will also be assessed.

5. Treatments and Assessments

Study participants will be treated with a single PAE procedure performed with Embosphere Microspheres. The microspheres will be mixed with a contrast agent and will be delivered to the arteries supplying the prostate via a microcatheter. The occlusion endpoint will be stasis as defined as persistent contrast in the feeding vessel that persists for 5 heartbeats. A complete description of the technical protocol to be followed is provided in Appendix C.

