5.2 Visit 1: Prostate Artery Embolization (PAE)

The PAE procedure will be performed within 4 weeks of baseline prostate ultrasound. PAE with Embosphere Microspheres will be performed according to the technical procedure provided in Appendix C.

Treatment data recorded will include the following:

- Total fluoroscopy time
- Total radiation dose
- Number and origins of arterial supply
- Volume and size of embolic material delivered
- Evidence of collateral blood supply
- Duration of hospitalization
- Sedative medications administered
- Patient pain score before and after procedure

- Procedure adverse events

5.3 Visits 2, 3, 4: 1 Month, 6 Months, 12 Months (4 weeks, 24, 52 ± 2 weeks post PAE)

Patients will have the following assessments performed:

- Physical exam, including vital signs
- IPSS and IIEF questionnaires
- TRUS of the prostate
- TAUS of the bladder
- Laboratory evaluations, including a complete blood count (CBC), complete metabolic panel (CMP), urinalysis, urine culture, and prostate specific antigen (PSA)
- Uroflowmetry to assess Qmax
- Cystoscopy, if clinically indicated
- Proctoscopy, if clinically indicated
- Review of concomitant medications and adverse events

Patients who are unable or unwilling to return for follow-up will be contacted by telephone, email, or mail to administer the IPSS and IIEF questionnaires, and to report any new treatments for BPH and/or LUTS.

5.4 Visit 5 (Long Term Follow-Up): 24 Months (104 ± 2 weeks post PAE)

Patients will have the following assessments performed:

- Physical exam, including vital signs
- IPSS and IIEF questionnaires
- TRUS of the prostate
- TAUS of the bladder
- Laboratory evaluations, including a complete blood count (CBC), complete metabolic panel (CMP), urinalysis, urine culture, and prostate specific antigen (PSA)
- Uroflowmetry to assess Qmax

Patients who are unable or unwilling to return for follow-up will be contacted by telephone, email, or mail to administer the IPSS and IIEF questionnaires, and to report any new treatments for BPH and/or LUTS.

6. Withdrawal of Patients

Patients will be informed that they have the right to withdraw from the study at any time for any reason, without prejudice to their medical care. The Investigator also has the right to withdraw patient from the study for any of the following reasons:

- Adverse event
- Concurrent medical condition
- Patient unwillingness to comply with study requirements
- Patient death
- Other Investigator decision

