9.2 Sample Size Calculations

This is a phase I/II, single center, prospective, single arm, investigational study to evaluate the safety and efficacy of prostate artery embolization (PAE) for treatment of severe LUTS related to BPH in patients with prostate size between 40 and 300 cm³ that have either failed or are intolerant to medical management. Twenty patients treated with PAE with Embosphere Microspheres are considered sufficient to provide data that will be used to evaluate the study objectives. No formal sample size calculations have been performed.

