9.5.1 International Prostate Symptom Score (IPSS)

The primary efficacy outcome will be based on the IPSS. The IPSS is a frequent used, validated, 8 item (7 symptom burden questions and 1 quality of life question) instrument which can be serially performed to compare the progression of symptoms and their severity over months and years. Patients are asked to assess how often they have experienced the following 7 symptoms in the past month: incomplete emptying, frequency, intermittency, urgency, weak urine stream, straining and nocturia. The response categories range from 0=Not at all to 5=Almost always. The total IPSS score is calculated by summing the responses for the 7 symptom burden items. The eighth item is an assessment of patient quality of life due to LUTS and does not contribute to the IPSS score calculation.

Patients will be classified into one of 3 symptom severity categories based on their total IPSS score as follows:

- Mildly symptomatic: 0-7
- Moderately symptomatic: 8-19
- Severely symptomatic: 20-35

The IPSS total score will be summarized for the baseline, 1 month, 6 month and 12 month time points, including change from baseline. Change from baseline will be calculated as post baseline IPSS score minus baseline IPSS score. A negative value indicates symptom improvement. 95% confidence intervals will be calculated for the mean change from baseline to the post baseline time points. For informational purposes, IPSS scores will also be summarized separately for patients that receive unilateral and bilateral PAE if there are sufficient numbers in both groups.

The primary efficacy analysis will be the change in IPSS total score from baseline to 12 months post PAE for the ITT population. A Paired-Sample Wilcoxon Signed Rank Test will be used to assess the statistical significance of the change from baseline to 12 months post PAE. A secondary analysis of the proportion of patients who have improved by at least one IPSS symptom category (i.e., severe to moderate, severe to mild, or moderate to mild) from baseline to 12 months post PAE will also be performed. A 95% confidence interval will be calculated for the proportion. The proportion of patients improving at least 3 points on the IPSS total score at the 12 month time point will also be summarized and the corresponding 95% confidence interval will be calculated.

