Appendix A: Schedule of Events

	Visit -1	Visit 1	Visit 2	Visit 3	Visit 4	Visit 5
	Screening/ Baseline (within 4 weeks of Day 1)	Treatment (Day 1)	Month 1 (4 weeks ± 2 weeks)	Month 6 (24 weeks ±2 weeks)	Month 12 (52 weeks ± 2 weeks)	Month 24 (104 weeks ± 2 weeks)
Informed Consent	X					
Eligibility criteria assessment	X					
Demographics	X					
Transrectal Ultrasound	X		X	X	X	X
Transabdominal Ultrasound	X		X	X	X	X
Medical History	X					
Concurrent Medical Conditions	X					
Physical Examination	X		X	X	X	X
Vital signs	X		X	X	X	X
Blood tests	X		X	X	X	X
Urinalysis	X		X	X	X	X
PSA	X		X	X	X	X
IPSS	X		X	X	X	X
IIEF	X		X	X	X	X
Uroflowmetry	X		X	X	X	
PAE		X				
Cystoscopy			X ¹	X ¹	X ¹	
Proctoscopy			X ¹	X ¹	X ¹	
Adverse Events		X	X	X	X	
Concomitant Medications	X	X	X	X	X	
Protocol violations	X	X	X	X	X	

¹ Cystoscopy and/or anoscopy will be performed for signs or symptoms of bowel or bladder injury, including hematuria, blood per rectum, or greater than expected pelvic pain at any time during the study protocol.

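### Section 4 requires a medication review at month 24 that Section 5.4, Appendix A and Section 9.7 omit, and only men who do not return are explicitly asked about new BPH/LUTS treatment

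*Combined protocol and SAP*

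**What the plan says.** Section 4 (Study Design) states that "patients will return for follow-up visits at 1, 6, 12, and 24 months post PAE" and lists what happens at each of them. The list ends with "uroflowmetry and laboratory evaluations, and medication and adverse event reviews". On that text, medication is reviewed at month 24.

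Section 5.3 (months 1, 6 and 12) carries this through: its in-person list closes with a review of medications and adverse events. Section 5.4 (month 24) lists physical exam, questionnaires, the two ultrasounds, laboratory tests and uroflowmetry, and has no such line.

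Both 5.3 and 5.4 add that men who cannot or will not return are contacted remotely "to administer the IPSS and IIEF questionnaires, and to report any new treatments for BPH and/or LUTS". Neither in-person list contains that question.

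In Appendix A the row "Concomitant Medications" is marked at screening, at treatment and at months 1, 6 and 12, and is blank at Visit 5. Section 9.7 defines the month-24 data by reference to 5.4.

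Objective 2.1 is IPSS improvement "in 20 patients with 24 months follow-up". Section 9.5.1 sets the formal analysis earlier: "The primary efficacy analysis will be the change in IPSS total score from baseline to 12 months post PAE for the ITT population".

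**The concern.** This is a single-arm study, so no control group absorbs the effect of other treatment. A man whose symptoms return and who then starts a drug or has a procedure may score well at month 24 for reasons unrelated to embolization. The remote-contact wording suggests that the authors regard new treatment as relevant to reading the IPSS. Yet the question is explicitly put only to men who miss the visit, and not to those who attend as planned.

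At stake is the reading of durability, which the background section names as an open question and which the 24 months in objective 2.1 are there to address. If a retreatment is not recorded at the visit, it may be hard to recover reliably afterwards.

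**Working it through.** **No stated figure to reproduce.** The point concerns data collection, and Section 9.2 says "No formal sample size calculations have been performed". The check is a comparison of sections, followed by an illustration of scale.

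**Step 1. Medication review at month 24, by section.**

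| Place | Month 24, man attends | Month 24, man does not attend |
|---|---|---|
| Section 4 | Medication review required | Not addressed |
| Section 5.4 | No medication review; no new-treatment question | New-treatment question asked |
| Appendix A, Visit 5 | Concomitant-medication row blank | Not addressed |
| Section 9.7 | Refers to 5.4 | Refers to 5.4 |

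Section 4 conflicts with the other three. Within 5.4, attenders and non-attenders are treated differently.

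**Step 2. Could another route capture retreatment after month 12?**
- Adverse events: Sections 7.1 and 7.2 set the recording period at 12 months, and the Appendix A row is blank at Visit 5.
- Serious adverse events: Section 7.1 does not count elective surgical procedures.
- Protocol violations: the Appendix A row is blank at Visit 5.
- Unscheduled visits: Section 9.1 leaves such data out of listings and tables unless otherwise specified.

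None of these clearly fills the gap.

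**Step 3. Is there an analysis rule?** Section 9.5.7 deals with missing data and outliers only. Section 9.6.5 puts concomitant medications in listings. No section says how an IPSS value obtained after a new BPH treatment is handled, at month 12 or at month 24.

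**Step 4. Scale per man (illustration).** If one of n men gains D extra IPSS points from an unrecorded retreatment, the mean change shifts by D / n. Here n = 20 (objective 2.1). D is assumed, with a range of 5 to 15 points, because the documents give no value.
- D = 5: 5 / 20 = 0.25 points
- D = 10: 10 / 20 = 0.50 points
- D = 15: 15 / 20 = 0.75 points

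For two such men the range is 0.5 to 1.5 points. For three it is 0.75 to 2.25. If fewer than 20 men have a month-24 score, n falls and the shift per man rises.

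**Step 5. How many men?** The documents do not say. The background cites a 255-patient series with clinical success of 75.2% at 1 year and 72% at 2 years.
- Without success at 1 year: (1 − 0.752) × 20 = 4.96 men
- Without success at 2 years: (1 − 0.72) × 20 = 5.6 men
- Net difference: (0.752 − 0.72) × 20 = 0.64 men

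The 5.6 is not a count of unrecorded retreatments. Failure is not retreatment, and any drug started by month 12 falls under the 5.3 review. The 0.64 is not an upper limit either, because a man who failed in year 1 may first be retreated in year 2. The number therefore stays unknown, and only the per-man shift is usable.

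**The case against.** The strongest reply is that Section 4 already requires the review, so the plan does provide for it, and the CRF, which is not in the documents, may have the field. This stands to the extent that one cannot say nobody asks attenders at month 24. What remains is an internal contradiction, in which the three places most likely to shape the month-24 CRF point the other way.

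A second reply is that the reach is small. The primary test and both IPSS responder proportions are at 12 months. Under Section 9.7 the month-24 data are summarized separately, and only selected items, optionally. This stands in full. A reader might infer a shift of 5 percentage points per man in a 24-month responder rate, but the plan contains no such analysis.

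A reader might also infer that IPSS after retreatment is counted as an effect of embolization. No section says so. The text supports only that the two cannot be told apart, because retreatment may go unrecorded and no handling rule exists. The missing rule applies at month 12 too, so an added question at month 24 would not cure it alone.

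Exclusion criterion 16 says of background prostate medication that "dose should not be adjusted during the study period". One might conclude that compliance goes unchecked after month 12. That is not established: Section 9.7 speaks of an initial 12-month study period, so the restriction may end there, and if it runs on, Section 4's review would cover it.

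Finally, a lighter long-term visit may be deliberate. Men also enter only if medical management has failed or was not tolerated and surgery is refused or ruled out, which makes it less safe to assume that every failure is retreated. Neither fact explains why non-attenders are asked and attenders are not.

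**Conclusion.** The contradiction between Section 4 and Sections 5.4, 9.7 and Appendix A is certain from the text, as is the uneven new-treatment question within 5.4. The consequence is conditional. If the trial follows 5.4, Appendix A and 9.7, retreatment after month 12 in attending men is not recorded, and their 24-month IPSS, Qmax and PVR cannot be separated from the effect of other treatment. This weakens the 24-month follow-up in objective 2.1 and leaves the 12-month primary test untouched.

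The total size is unknown. The per-man shift of 0.25 to 0.75 IPSS points rests on 20 men contributing and on an assumed gain of 5 to 15 points. It should be corrected, as a matter of moderate importance.

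**What to change.** 1. Reconcile Section 4, Section 5.4, Section 9.7 and Appendix A: add concomitant-medication review to the 5.4 in-person list and mark it at Visit 5 in Appendix A. Section 9.7 then follows through its reference to 5.4.
2. In 5.3 and 5.4, ask every man, attending or remote, at every follow-up visit about new treatments for BPH or LUTS (drug, dose change or procedure), and record the date of each.
3. In Section 9, report the number of men retreated, and show IPSS change at months 12 and 24 both including and excluding values after retreatment. Both are needed: the first contains the effect of other treatment, and the second drops men who may have done worst. State whether an excluded value counts as missing, and so would be filled by LOCF under 9.5.7.

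The cost is one CRF item, one mark in the schedule and a short addition to the analysis text, with no new visit or test. The downside for the sponsor is that the 24-month result may look less favourable once retreated men are identified.

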7.1 Definitions

Adverse Event: An adverse event (AE) is any untoward medical occurrence in a patient, and does not necessarily have a causal relationship with the treatment. An AE therefore can be any unfavorable or unintended sign (including a clinically significant abnormal laboratory finding, for example), symptom, or disease temporally associated with the use of a medicine or procedure, whether or not considered related to the product or procedure. A non-serious AE is any untoward medical occurrence that does not meet any of the criteria for a serious adverse event as defined below.

Laboratory data will be collected as described in this protocol. Clinical syndromes associated with laboratory abnormalities are to be recorded as appropriate (e.g., diabetes mellitus instead of hyperglycemia).

Patients will be instructed to report any AE that they experience to the Investigator or Study Coordinator. AEs will be assessed at each visit. AEs occurring during the clinical trial and the protocol-defined 12 month follow-up period will be recorded and reported on the AE CRF. In order to capture the most potentially relevant safety information during this study, the Investigator will record AE terms accurately and consistently throughout the study. Wherever possible, a specific disease or syndrome will be reported on the CRF rather than the associated signs and symptoms. If observed or reported signs or symptoms are not considered a component of a specific disease or syndrome by the Investigator they should be recorded as separate AEs on the AE CRF.

All adverse events will be assessed for severity, relationship to the study treatment, relationship to the study device, treatment required, and outcome/resolution. This information will be recorded and reported on the Adverse Event CRF (3500A).

Adverse events that might occur in this study include, but are not limited to:

- For cystoscopy and PAE: Burning sensation in the urethra, urinary infection, hematuria, pain
- General embolization risks: fever, hypotension, hypertension, arterial thrombosis and occlusion, pseudoaneurysm, risks of conscious sedation, amputation, and death.
- For PAE: Hematospermia, hemorrhage, injury to the bladder (including the bladder neck, ureteral orifice or trigone), impact on future fertility, vasospasm, rectorrhagia, inguinal hematoma, bladder/bladder neck ischemia and necrosis leading to bladder resection, balanitis, erectile dysfunction, rectal ischemia, rectal injury, allergic reaction to Embosphere Microspheres or contrast agent, radiation exposure, vascular perforation, need for subsequent surgery to repair non-target ischemia, and sensory abnormality

Serious Adverse Event: A serious adverse event (SAE) is any adverse event, occurring at any dose and regardless of causality that:

- Results in death
- Is life-threatening, such that the patient was at immediate risk of death from the event as it occurred (i.e., it does not include a reaction which hypothetically might have caused death had it occurred in a more severe form)
- Requires inpatient hospitalization or prolongation of existing hospitalization. Hospital admissions and/or surgical operations scheduled to occur during the study period but planned prior to study entry are not considered AEs if the illness or disease existed before the patient was enrolled in the study, provided that the patient's condition does not deteriorate in an unexpected manner during the study (e.g., surgical procedure performed earlier than planned)
- Results in persistent or significant disability/incapacity, such that the patient experiences a substantial disruption of their ability to conduct normal life functions

- Is an important medical event as determined by the Investigator. An important medical event is an event that may not result in death, be life-threatening, or require hospitalization, but may be considered an SAE when, based upon appropriate medical judgment, it may jeopardize the patient and may require medical or surgical intervention to prevent one of the outcomes listed above. Examples of such medical events include allergic bronchospasm requiring intensive treatment in an emergency room or at home, blood dyscrasias or convulsions that do not result in inpatient hospitalization, or the development of drug dependency or drug abuse.

Clarification should be made between the terms “serious” and “severe” since these are not synonymous. The term “severe” is often used to describe the intensity (severity) of a specific event (as in mild, moderate or severe myocardial infarction); the event itself, however, may be of relatively minor medical significance (such as a severe headache). This is not the same as “serious,” which is based on event outcome or action criteria described above and is usually associated with events that pose a threat to a patient’s life or ability to function. A severe adverse event does not need to be considered serious. For example, persistent nausea of several hours duration may be considered severe nausea but not constitute an SAE unless the patient is admitted to the hospital or the event meets any other criteria for seriousness. On the other hand, a stroke resulting in only a minor degree of disability may be considered mild, but would be defined as an SAE based on the criteria described above. Seriousness (not severity) serves as a guide for defining regulatory reporting mechanisms.

Under this protocol, scheduled hospitalizations or elective surgical procedures will not be considered SAEs. Prolongation of a scheduled hospitalization will be considered an SAE as described above. Complications associated with surgical procedures or study treatments resulting in one of the outcomes above are considered SAEs.

